## **8. RESEARCH QUESTION AND OBJECTIVES**

The primary objective of this study is to assess the incidence rate (overall and age stratified) of emergency surgery and major bleeding associated with fracture and trauma among patients to characterize the incidence of relatively homogeneous population who undergo oral anticoagulants (OAC) therapy.

The secondary objective is to estimate the incidence rate (overall and age stratified) of cardiac tamponade or pericardiocentesis occurring during or within one day after conducting a PCI or cardiac ablation procedure.

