### **9.3.2      Outcomes**

#### **9.3.2.1     Primary outcomes**

- Outcome name: A combined endpoint of three outcomes; 1) emergency surgery, (2) major bleeding due to fracture (3) major bleeding due to trauma
- Definition: each events will be defined as following:
  - (1) Emergency Surgery defined as any surgical procedure(International Classification of Diseases (ICD) 10 code K000-879) performed on the same day as hospital admission with additional claims associated with urgent fee MDV codes (114701370, 160000210, 180709110)
  - (2) Major bleeding due to fracture  
Any bleeding associated with hospitalization or blood transfusion (ICD10 code E83.111) accompanied by any fracture (M484, M80, S021, S12, S22, S32, S42, S52, S62, S72, S82, S92, T02, T08, T10, T12, T142) listed as the primary diagnosis requiring most medical resource
  - (3). Major Bleeding due to trauma  
Any bleeding associated with hospitalization or blood transfusion (ICD10 code E83.111) accompanied by any trauma (S00-S09, I620, M125, M164, M165, M172, M173, M191, M483, M872, S065, S066, S081, S089, S130, S18, S230, S480, S481, S532, S533, S580, S581, S589, S633, S634, S680, S681, S684, S688, S689, S780, S789, S889, S980, S981, S982, T050, T053, T058, T059, T116, T136, T147, T794, T795, T796, T797, S271, S272, S330, S334, S382, S480, S481, S532, S580, S581, S589, S633, S634, S680, S681) listed as the primary diagnosis requiring most medical resource

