### **9.3.3 Covariates**

These covariates will be used as patient characteristics for the overall population with the primary outcome events.

1. History of stroke or transient ischemic attack yes/no
2. History of myocardial infarction yes/no
3. History of heart failure yes/no
4. History of diabetes mellitus yes/no
5. History of dyslipidemia
6. History of arterial hypertension yes/no
7. History of peripheral artery disease
8. History of kidney impairment
9. History of valvular disease
10. History of liver disease
11. History of dementia
12. History of trauma
13. History of fracture
14. Nursing home resident
15. History of bleeding
16. Charlson co-morbidity index [3]
17. Concomitant medication yes/no for the following:
  - a. aspirin
  - b. clopidogrel
  - c. angiotensin receptor blockers (ARB) or angiotensin converting enzyme inhibitors (ACE)
  - d. beta-blocker
  - e. amiodarone
  - f. calcium-channel blocker (CCB)
  - g. diuretics
  - h. statins
  - i. proton-pump inhibitor
  - j. H2 receptor antagonist

The disease, Charlson co-morbidity index and concomitant medication are defined as [Table 1-Table 4](#). Nursing home resident is defined as MDV codes 113011710, 113016010, 114020910.

Table 1

Definition of clinical history

Disease	Definition	
	ICD10code	prescription
Stroke or transient ischemic attack	I60-I64, G45	-
Myocardial infarction	I21-I23	-
Heart failure	I110, I130, I132, I420, I50	Prescribed furosemide (defined by generic name)
Diabetes mellitus	E100, E101, E109, E110, E111, E119, E14	Prescribed drugs used in diabetes (defined by Anatomical Therapeutic Chemical (ATC) code as A10)
Dyslipidemia	E78	-
Arterial hypertension	I10-I15	Prescribed 2 or more types of anti-hypertensive (defined in Table 2 )
Peripheral artery disease	I702-I709, I71, I739	-
Kidney impairment	N28	-
Valvular disease	I059, I089, I358, I38, I48	-
Liver disease	K70-K77	-
Dementia	F00-F03, G30	-
Trauma	S00-S09, I620, M125, M164, M165, M172, M173, M191, M483, M872, S065, S066, S081, S089, S130, S18, S230, S480, S481, S532, S533, S580, S581, S589, S633, S634, S680, S681, S684, S688, S689, S780, S789, S889, S980, S981, S982, T050, T053, T058, T059, T116, T136, T147, T794, T795, T796, T797, S271, S272, S330, S334, S382, S480, S481, S532, S580, S581, S589, S633, S634, S680, S681	-
Fracture	M484, M80, S02, S12, S22, S32, S42, S52, S62, S72, S82, S92, T02, T08, T10, T12, T142	-

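### Primary outcome (3) is worded as bleeding with any trauma, but its code list covers the whole head and only selected injuries below it, so major bleeding from trauma below the head is under-ascertained; the net bias in the rate is unknown

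*Combined protocol and SAP*

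**What the plan says.** Section 9.3.2.1, outcome (3), counts bleeding with hospitalisation or transfusion when it is "accompanied by any trauma (S00-S09, I620, M125" and so on, with the trauma code "listed as the primary diagnosis requiring most medical resource". After the head block come I620 and eight M codes. The injuries below the head are then "S130, S18, S230, S480, S481, S532, S533, S580, S581, S589, S633, S634, S680, S681, S684, S688, S689, S780, S789, S889, S980, S981, S982", followed by "T050, T053, T058, T059, T116, T136, T147" and "T794, T795, T796, T797, S271, S272, S330, S334, S382". Ten of the limb codes are then printed a second time. The bleeding itself has no diagnosis code list in this section.

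Table 1 in Section 9.3.3 uses the same list for history of trauma (for example "S780, S789, S889, S980, S981, S982, T050, T053").

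The scope is stated in two ways. Section 8 speaks of "emergency surgery and major bleeding associated with fracture and trauma", with no body region named, and the title page and the objectives in the abstract agree with it. The rationale in the abstract and Section 7 both limit the aim to fracture and head trauma.

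Sections 9.9 and 9.12 admit that the codes are unvalidated and their accuracy unknown. They do not say that injury types or body regions are left out.

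**The concern.** The list acts as a gate: an injury that is not on it cannot make a bleed a trauma event, however severe the bleed. A patient on an anticoagulant who is admitted and transfused for a ruptured spleen, a liver laceration or a limb-artery injury, with that injury as the main diagnosis, is not counted under outcome (3). Under the follow-up rule in Section 9.2 the patient-time stays in the denominator.

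The study is meant to describe the medical need for anticoagulant reversal, and these bleeds are central to it. A reader shown a rate for bleeding due to any trauma, overall and by age, would not know that they were left out. The history-of-trauma covariate has the same gap.

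**Working it through.** **Plan's own figures.** The documents give no expected trauma-bleeding rate, event count or precision target. The cohort size in Section 9.5 reproduces: 7,441 + 23,412 + 16,026 + 12,779 + 3,230 = 62,888. The mean follow-up also agrees: 121 / 365.25 = 0.331 year, against about 0.3 year.

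**Step 1: count the list in 9.3.2.1 (3).** There are 63 entries. Ten are duplicates, leaving 63 − 10 = 53. These are 5 head entries (S00-S09 and four codes already inside it), 9 I and M codes, and 53 − 5 − 9 = 39 S and T codes below the head.

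**Step 2: classify the 39.** The protocol prints no code titles. Standard ICD-10 headings are assumed here and must be confirmed in the Japanese code master.

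| Class | Codes | Number |
|---|---|---|
| Amputation | S18 (1), S48 (2), S58 (3), S68 (5), S78 (2), S88 (1), S98 (3), T05 (4), T116, T136, S382 | 24 |
| Disc rupture | S130, S230, S330 | 3 |
| Ligament or symphysis rupture | S532, S533, S633, S634, S334 | 5 |
| Haemothorax or haemopneumothorax | S271, S272 | 2 |
| Early complications of trauma | T794 to T797 | 4 |
| Crush or amputation, region unspecified | T147 | 1 |

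The first four rows give 24 + 3 + 5 + 2 = 34, and 34 / 39 = 87%.

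**Step 3: look for what is missing.** S10 to S99 holds 90 three-character categories. One (S18) is listed in full. Thirteen are listed in part (S13, S23, S27, S33, S38, S48, S53, S58, S63, S68, S78, S88, S98). Nine are in the fracture list (S12, S22 and so on to S92). That leaves 90 − 1 − 13 − 9 = 67 in neither list. Those absent include:

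- vessels: S15, S25, S45, S55, S65, S75, S85, S95 and, for the abdomen and pelvis, S35
- heart: S26
- abdominal and pelvic organs: S36, S37
- crush below the head: S17, S28, S47, S57, S67, S77, S87, S97.

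Also absent are T00, T01, T03, T04, T06, T07 and T09 (mainly multiple injuries). S27 appears only as two sub-codes.

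**Step 4: direction.** For a listed definition, observed rate = true rate × sensitivity / PPV. Missing codes lower sensitivity. PPV may also be below 1. By its standard heading I620 is non-traumatic subdural haemorrhage. The eight M codes are late or post-traumatic joint, spine and bone disease. S00-S09 also contains skull fractures, including S021, which belongs to the fracture outcome.

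The following is an illustration only. It assumes a true rate of 2 per 1,000 patient-years and 62,888 × 0.3 = 18,866 patient-years, hence 37.7 true events. Section 9.5 expects follow-up to be longer than 0.3 year; the ratios do not depend on it.

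| Sensitivity | Events counted, PPV 1.0 | Events counted, PPV 0.7 |
|---|---|---|
| 0.9 | 34.0 (10% too low) | 48.5 (too high) |
| 0.7 | 26.4 (30% too low) | 37.7 (unbiased) |
| 0.5 | 18.9 (50% too low) | 27.0 (too low) |

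The same omission can go with a rate that is too high, right or too low.

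**The case against.** A reader might infer that the reported trauma rate must be too low. The documents do not support that. It holds only if sensitivity is below PPV, and Section 9.9 says that accuracy is unknown. The listed codes that inflate the count, and the uncoded bleeding term, work the other way.

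A reader might also infer that every such patient is event-free in the combined endpoint. That is too strong. A splenic or arterial injury operated on the admission day with an urgent-fee claim counts as emergency surgery. A multiply injured patient whose main diagnosis is a head injury or a listed fracture can enter under outcome (3) or (2).

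Nor are crush and multi-region injuries wholly missing: T147, four T05 sub-codes and head crush inside S00-S09 are listed.

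The count of 67 categories measures coverage, not lost bleeds. By standard headings at least 20 of them are nerve or cord (9), muscle or tendon (7) or joint injuries (4), which are not the bleeding injuries at issue.

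Finally, the complete head block could reflect the head-trauma wording in the abstract's rationale and Section 7. That explains it only in part, since the list also holds limb, thoracic and pelvic codes and the objectives are not limited to the head.

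All of this limits what can be said about direction, size and the combined rate. None of it makes the list match the name of the outcome, and the limitations sections do not disclose the gap.

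**Conclusion.** The point holds as a mismatch between a primary outcome and its codes. Outcome (3) claims any trauma, but below the head its list consists mostly (34 of 39 codes) of amputations, disc or ligament ruptures and haemothorax, and it leaves out the vessel, heart and abdominal or pelvic organ categories. The trauma component therefore under-ascertains major bleeding from trauma below the head.

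Taken alone, the omission can only lower the rate. The net bias has unknown sign and size, because the documents give neither a trauma-bleeding rate nor the share of bleeds under the omitted codes. The combined endpoint is affected less than the trauma component. The code counts come directly from the printed list. The meaning of the codes rests on standard ICD-10 headings.

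**What to change.** First reconcile head trauma (abstract rationale, Section 7) with trauma (title page, abstract objectives, Sections 8 and 9.3.2.1).

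If all trauma is meant:

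- Add to the existing list at least S15, S25, S26, all of S27, S35-S37, S45, S55, S65, S75, S85, S95, the crush categories named above, and T00, T01, T03, T04, T06, T07 and T09.
- Keep T794-T797. Replacing the list wholesale with S00-S99 and T00-T14 would drop them and admit many injuries that rarely bleed.
- Exclude the fracture codes used for outcome (2).
- Use the same list in the Trauma row of Table 1, and confirm all titles in the Japanese code master.
- Report head and non-head trauma separately, with the current list as a sensitivity analysis.

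If only the listed injuries are meant, rename the outcome for what the list covers and state the omission in Section 9.9.

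The cost is a little extra programming and no new data. Counts will differ from any earlier run on the short list. Some specificity may be lost, the more so while bleeding has no code list of its own.

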#### **9.3.2.2     Secondary outcomes**

Outcome name: cardiac tamponade and pericardiocentesis

Event Definition:

- (1). Cardiac tamponade diagnosis (ICD 10 code 4200001) on the same or next day as catheter ablation or PCI (MDV procedure codes 150153910, 150267810, 150263310, 150284310, 150303310, 150345710, 150374910, 150375010, 150375210, 150375310, 150375410)
- (2). Pericardiocentesis (MDV procedure code 140010510) on the same or next day as catheter ablation or PCI (MDV procedure codes as above)

### **9.3.3 Covariates**

These covariates will be used as patient characteristics for the overall population with the primary outcome events.

1. History of stroke or transient ischemic attack yes/no
2. History of myocardial infarction yes/no
3. History of heart failure yes/no
4. History of diabetes mellitus yes/no
5. History of dyslipidemia
6. History of arterial hypertension yes/no
7. History of peripheral artery disease
8. History of kidney impairment
9. History of valvular disease
10. History of liver disease
11. History of dementia
12. History of trauma
13. History of fracture
14. Nursing home resident
15. History of bleeding
16. Charlson co-morbidity index [3]
17. Concomitant medication yes/no for the following:
  - a. aspirin
  - b. clopidogrel
  - c. angiotensin receptor blockers (ARB) or angiotensin converting enzyme inhibitors (ACE)
  - d. beta-blocker
  - e. amiodarone
  - f. calcium-channel blocker (CCB)
  - g. diuretics
  - h. statins
  - i. proton-pump inhibitor
  - j. H2 receptor antagonist

The disease, Charlson co-morbidity index and concomitant medication are defined as [Table 1-Table 4](#). Nursing home resident is defined as MDV codes 113011710, 113016010, 114020910.

Table 1

Definition of clinical history

Disease	Definition	
	ICD10code	prescription
Stroke or transient ischemic attack	I60-I64, G45	-
Myocardial infarction	I21-I23	-
Heart failure	I110, I130, I132, I420, I50	Prescribed furosemide (defined by generic name)
Diabetes mellitus	E100, E101, E109, E110, E111, E119, E14	Prescribed drugs used in diabetes (defined by Anatomical Therapeutic Chemical (ATC) code as A10)
Dyslipidemia	E78	-
Arterial hypertension	I10-I15	Prescribed 2 or more types of anti-hypertensive (defined in Table 2 )
Peripheral artery disease	I702-I709, I71, I739	-
Kidney impairment	N28	-
Valvular disease	I059, I089, I358, I38, I48	-
Liver disease	K70-K77	-
Dementia	F00-F03, G30	-
Trauma	S00-S09, I620, M125, M164, M165, M172, M173, M191, M483, M872, S065, S066, S081, S089, S130, S18, S230, S480, S481, S532, S533, S580, S581, S589, S633, S634, S680, S681, S684, S688, S689, S780, S789, S889, S980, S981, S982, T050, T053, T058, T059, T116, T136, T147, T794, T795, T796, T797, S271, S272, S330, S334, S382, S480, S481, S532, S580, S581, S589, S633, S634, S680, S681	-
Fracture	M484, M80, S02, S12, S22, S32, S42, S52, S62, S72, S82, S92, T02, T08, T10, T12, T142	-
Bleeding (gastro-intestinal, etc.)	K25-K29, K922, R04, R31, R58, K250, K260, K270, K280, K290, S063, S064, S065, S066	-

Table 2

Definition of anti-hypertensive

Class/type	ATC code
CCB	C08A0
ARB	C09C0
ACE	C09A0
Diuretics	C03A1, C03A2, C03A3, C03A7, C03A9
Thiazide diuretic	C03A3 (Thiazide, plane), C02D0 (Rauvolfia alkaloids)
Beta blocker	C07A0
Alpha-adrenoreceptor antagonists	C02A2
Potassium-sparing agents	C03A1
Others	C02A1 (Antihypertensives), C02A3 (Antihypertensives for pulmonary arterial hypertension), C09X0 (Other agents acting on the renin-angiotensin system)
Combination agents	C09D1 (ARB and diuretics), C09D3 (ARB and CCB)

Table 3

Definition of disease/conditions and weighted index for Charlson co-morbidity score

Score	Desease/conditions	Definition (ICD-10 code)
1	Myocardial infarct	See Table 1
1	Congestive heart failure	I110, I130, I132, I500
1	Peripheral vascular disease	I70-I74, I77
1	Cerebrovascular disease	I60-69
1	Dementia	See Table 1
1	Chronic pulmonary disease	J40-J47, J60-J67, J684, J701, J703, J841, J920, J961, J982, J983
1	Connective tissue disease	M05, M06, M08, M09, M30-M36, D86
1	Ulcer disease	K221, K25-K28
1	Mild liver disease	B18, K700-K703, K709, K71, K73, K74, K760
1	Diabetes mellitus	See Table 1
2	Hemiplegia	G81, G82
2	Moderate/severe renal disease	I12, I13, N00-N05, N07, N11, N14, N17-N19, Q61
2	Diabetes mellitus with chronic complications	E102-E018, E112-E118
2	Any tumor	C00-C75
2	Leukemia	C90-C96
2	Lymphoma	C81-C85, C88, C90, C96

Table 3 (cont'd)

Score	Desease/conditions	Definition (ICD-10 code)
3	Moderate/severe liver disease	B150, B160, B162, B190, K704, K72, K766, I85
6	Metastatic solid tumor	C76-C80
6	AIDS	B21-B24

Table 4 Definition of concomitant medication

Drug	Definition	
	ATC code	Generic name
Aspirin	-	Aspirin, aspirin dihydroxyaluminum aminoacetate magnesium carbonate
Clopidogrel	-	Clopidogrel sulfate
ARB or ACE	C09A0, C09C0, C09D1	-
Beta blocker	C07A0	-
Amiodarone	-	Amiodarone hydrochloride
CCB	C08A0	-
Diuretics	C03A1, C03A2, C03A3, C03A7, C03A9	-
Statins	C10A1	-
Proton pump inhibitor	A02B2	-
H 2 receptor antagonist	A02B1	-

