Population:  Medical Data Vision (MDV) clinical database is used Oral anticoagulants (OAC) naïve, adult patients with NVAF initiating dabigatran, warfarin, apixaban, rivaroxaban or edoxaban between March 1, 2011 and June 30, 2016  Inclusion criteria: patients aged >18 year-old with confirmed diagnosis of NVAF (International Classification of Diseases (ICD) 10 I48), having a first prescription (index date) of any one of OACs (dabigatran, warfarin, rivaroxaban, apixaban or edoxaban) having no prescription of OACs for 6 months prior to the index date (this period is defined as the baseline period).  Exclusion criteria: patients having less than 6 months of enrolment prior to the index date, being dialysis or kidney transplant recipients in baseline period, having either atrial flutter, valvular atrial fibrillation (AF), mechanical valve placement, rheumatic AF, and/or mitral valve prolapse/regurge/stenosis in baseline period, and having record of deep			

Name of company: Boehringer Ingelheim			
Name of finished medicinal product: Prazaxa			
Name of active ingredient: Dabigatran etexilate			
Protocol date: 18 July 2017	Study number: 1321-0022	Version/Revision: 1.0	Version/Revision date: Not applicable
Variables: vein thrombosis or pulmonary embolism < 6months before AF diagnosis in baseline period.			
Data sources:	MDV clinical database. The database is health insurance claims database. As of end of February 2016, MDV has accumulated claims records from 12.94 million patients, both in and out-patients, from more than 230 large acute, sub-acute and outpatient care DPC hospitals.		
Study size:	The previous study 1160.279 has identified the patients with confirmed 6 months of baseline period and no OAC treatment (defining “treatment naïve” new starter population). The total of these patients was 62,888. The breakdown by OAC initiated was 7,441 for dabigatran, 23,412 for warfarin, 16,026 for apixaban, 12,779 for rivaroxaban and 3,230 for edoxaban. The mean on-treatment follow-up duration for all OACs new starters combined in patients with one year of baseline period was calculated as 121 days. The mean on-treatment follow-up duration for all OACs new starters combined with 6 months of baseline period is unknown.		

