## **9.7 DATA ANALYSIS**

### **9.7.1 Main analysis**

#### For the primary outcome

Incidence rate of emergency surgery and major bleeding due to fracture/trauma will be described with each number of patients with event, patient-year and 95% confidence interval overall and stratified by age (age <64, 65-74 and >75). Baseline characteristics of patients overall and stratified by age will be provided in a tabulated format.

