## 9.11 SUBJECTS

The source population is Japanese patients who have claims data in MDV commercial database. In order to have claims in the database, the patients must have received some medical intervention, out or in-patient hospital visit, or pharmacy prescription from the DPC hospitals in Japan. DPC hospitals are large hospitals, often associated with medical schools or government funding, providing both acute and chronic medical care in Japan. Compared to non-DPC hospitals, they tend to provide more specialized, intensive medical care in addition to outpatient primary care tending to chronic disease requiring non-urgent care. MDV database has contractual agreement to receive claims data from approximately 12% of all DPC hospitals in Japan, and the selection is based on the willingness on the side of DPC hospitals to receive either financial compensation or data services from MDV.

The inclusion and exclusion criteria are intended to select those Japanese atrial fibrillation patients who have non-valvular etiology and have newly initiated oral anti-coagulants for stroke prevention. The exclusion criteria also include patients on dialysis or kidney transplant and having records of deep vein thrombosis or pulmonary embolism to exclude those patients who are presumed to have high risk of bleeding and those receiving OAC for indications other than atrial fibrillation.

The data cut-off of 14 Mar 2011 to 30 June 2016 is to select those claims that have occurred after the launch of dabigatran and to the most recent available data cut from MDV at the time of protocol writing.

The availability of co-variates for matching was evaluated in the feasibility analysis of CTMS 1160.279. External validity was assessed by comparing the incidence of claims defined incidence of stroke, intracranial haemorrhage and systemic embolism in MDV database against previously reported prospective atrial fibrillation registry conducted in Japan by Koretsune et al [4]

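### Table 1 counts the AF inclusion code I48 as valvular disease, and Table 4 leaves combination tablets out of the ARB/ACE, CCB and diuretic rows

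*Combined protocol and SAP*

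**What the plan says.** The Abstract admits patients with a "confirmed diagnosis of NVAF (International Classification of Diseases (ICD) 10 I48" code. It excludes those with "valvular atrial fibrillation (AF), mechanical valve placement, rheumatic AF, and/or mitral valve prolapse/regurge/stenosis in baseline period". Section 9.11 confirms the aim of selecting "atrial fibrillation patients who have non-valvular etiology".

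Section 9.3.3 makes Tables 1 to 4 the operative definitions of disease history, Charlson index and concomitant medication. In Table 1 the Valvular disease row reads "I059, I089, I358, I38, I48", and its prescription column is empty.

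Table 2, which defines antihypertensive classes, labels its combination agents "C09D1 (ARB and diuretics), C09D3 (ARB and CCB". Table 4, which defines concomitant medication, gives ARB or ACE as "C09A0, C09C0, C09D1". Its CCB row contains C08A0 only, and its Diuretics row contains five C03A codes and nothing else.

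The covariates are descriptive. Section 9.7.1 makes the table an output of the main analysis: "Baseline characteristics of patients overall and stratified by age will be provided in a tabulated format".

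**The concern.** The code that makes a patient eligible as non-valvular is also one of the codes that label the patient as valvular. Followed literally, the baseline table would report a large amount of valvular disease in a cohort chosen to be free of the main forms of it. Patients carrying one of the other four codes could not be told apart from the rest.

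The medication fault is harder to notice. A valvular percentage close to 100 would probably prompt a query, whereas a CCB or diuretic percentage that is somewhat too low would look plausible and go through. The quality control in Section 9.8 checks the calculation and reviews the methodology, but a program that follows these tables faithfully would reproduce both faults.

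At stake is the description of who was studied, which readers of the planned publication will use to judge how the incidence rates apply to their own patients.

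**Working it through.** The plan states no figure on this point, so the check compares the printed code lists.

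**Valvular row**

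- Inclusion code (Abstract): {I48}.
- Valvular disease (Table 1): {I059, I089, I358, I38, I48}.
- Overlap: {I48}, that is 1 of the 5 codes.

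Assume that any one listed code sets the flag, which is the natural reading of a code list. Let p be the share of patients with one of the other four codes, and s the share whose I48 record falls in the baseline period, taken as independent of p. Then

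flag prevalence = p + (1 − p) × s.

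The documents give neither p nor s, so the values below are assumptions:

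- s = 0: the flag equals p, and I48 does no harm.
- s = 0.7, p = 0.02: 0.02 + 0.98 × 0.7 = 0.706.
- s = 0.9, p = 0.20: 0.20 + 0.80 × 0.9 = 0.92.
- s = 1: p + (1 − p) = 1, whatever p is.

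The excess over p is (1 − p) × s. Unless s is close to zero, the row mainly reports when AF was coded. With I48 removed, the flag equals p.

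**Combination tablets**

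Table 2's labels supply the components, so no outside drug dictionary is needed.

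- C09D3, ARB component: belongs in ARB/ACE; absent from Table 4.
- C09D3, CCB component: belongs in CCB; absent.
- C09D1, ARB component: belongs in ARB/ACE; present.
- C09D1, diuretic component: belongs in Diuretics; absent.

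Four entries are implied, one is present and three are missing. They fall in three of Table 4's ten rows. The direction is certain: a patient whose only ARB and only CCB come from a C09D3 tablet is recorded as taking neither, and one whose only diuretic is in a C09D1 tablet is recorded as taking none. A patient who also takes a listed single agent of the same class is still counted correctly.

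The documents give no usage frequency for either code. For scale only, in a cohort of the size quoted in Section 9.5, each 1% of patients so affected is 0.01 × 62,888 ≈ 629 people.

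**Typing error**

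Table 3 prints the range E102-E018 for diabetes with complications. Its end precedes its start, so it cannot be programmed as printed. The adjacent range E112-E118 suggests that two digits were transposed.

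**The case against.** The strongest reply is that nothing of consequence moves. Section 9.3.3 uses the covariates only to describe patients, Section 9.5 says that no hypothesis is formally tested, and no adjusted model is planned. That stands, and it limits the weight of the point. It does not remove it, because the baseline table is a stated output of the main analysis and would be wrong as specified.

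It could also be said that Table 4 deliberately counts single agents only. This fails: C09D1 is a combination, and Table 4 already counts it under ARB/ACE.

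A reader might infer more than the documents support in four respects.

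- **That the valvular flag is positive for everyone and carries no information.** This requires every qualifying I48 record to fall in the window. The Abstract defines a baseline period of six months before the index date but does not say when I48 must be recorded. A diagnosis first coded on the index date might fall outside it. The supportable statement is that the row does not measure valve disease.
- **That the kidney lists contradict each other.** Kidney impairment in Table 1 and moderate/severe renal disease in Table 3 share no code. However, Table 3 refers back to Table 1 where a list is meant to be shared, and it gives renal disease its own list. Different lists for different outputs are not a contradiction.
- **That the Charlson score is materially wrong.** Neither I48 in Table 1 nor the Table 4 omissions feed into Table 3. The only link is the evident typing error, which a programmer would be expected to query.
- **That the choice of patients described changes the valvular result.** Sections 9.3.3 and 9.7.1 word the group differently, but either group was admitted on I48.

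**Conclusion.** The point holds as a specification error in the descriptive baseline table. The Valvular disease row includes the inclusion code and so flags every patient whose I48 record lies in the baseline period. This assumes that one listed code is enough and that the baseline period is the window. Its size depends on the share of I48 records in that window, which the documents do not give; if that share were 70% to 90%, the row would read about 71% to 92% for a true share of 2% to 20%.

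Three of the four class entries implied by Table 2 are missing from Table 4. The ARB/ACE, CCB and Diuretics rows therefore err only downwards, by an amount that cannot be sized. Emergency surgery, bleeding and tamponade rates and their confidence intervals are unaffected. The lists should be corrected before programming, but the error does not threaten the study's objectives.

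**What to change.** - Table 1, Valvular disease: delete I48, or replace it with the code that was intended.
- Table 4: add C09D3 to ARB or ACE and to CCB, and add C09D1 to Diuretics.
- Table 3: correct the range E102-E018 at the same time.

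These are edits to lookup tables and need no new data. The one drawback is comparability: if study 1160.279 used the same lists, which the protocol does not say, the new baseline table may not match it line by line. The report should note the changed definitions.

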## 9.5 STUDY SIZE

This study plans no formal hypothesis testing.

The previous study 1160.279 has identified the patients with confirmed 6 months of baseline period and no OAC treatment (defining “treatment naïve” new starter population). The total of these patients was 62,888. The breakdown by OAC initiated was 7,441 for dabigatran, 23,412 for warfarin, 16,026 for apixaban, 12,779 for rivaroxaban and 3,230 for edoxaban. The average on-treatment follow-up period for pooled OAC in patients with at least one year of baseline period prior to index date excluding the time after switching from one OAC to another was approximately 0.3 year. The average on-treatment follow-up period for pooled

OAC including the time after switching with 6 months of baseline period is unknown, but should be longer than 0.3 year.

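### Table 1 counts any K25-K28 code as a history of bleeding, although Table 3 defines the same categories as ulcer disease, so tabulated prior bleeding is biased upward

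*Combined protocol and SAP*

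**What the plan says.** Section 9.3.3 lists "History of bleeding" as covariate 15 and sends the reader to the code tables: "The disease, Charlson co-morbidity index and concomitant medication are defined as" Tables 1 to 4. In Table 1 the Bleeding row reads "K25-K29, K922, R04, R31, R58, K250, K260, K270, K280, K290, S063, S064, S065, S066". Its prescription column holds only a dash, whereas heart failure, diabetes and hypertension each carry a prescription entry there.

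Table 3 in the same section defines ulcer disease, worth one Charlson point, by K221 together with the whole categories K25 to K28.

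On use, section 9.3.3 states: "These covariates will be used as patient characteristics for the overall population with the primary outcome events". Section 9.7.1 adds that baseline characteristics will be tabulated overall and by age group.

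The two major-bleeding outcomes in section 9.3.2.1 rest on "Any bleeding associated with hospitalization or blood transfusion", accompanied by a fracture or trauma as primary diagnosis. They give no bleeding diagnosis codes and do not refer to Table 1.

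**The concern.** The two tables give the same codes two different meanings. In Table 3 a code in K25 to K28 means that the patient has ulcer disease. In Table 1 the same code means that the patient has bled. Nothing in the Bleeding row, neither a prescription condition nor a restriction to sub-codes, separates an ulcer that bled from one that did not.

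What is at stake is a baseline figure. The study asks how often anticoagulated patients reach situations in which reversal might be needed, and readers will use the prior-bleeding row to judge what kind of patients these are. As defined, that row reports bleeding or any K25-K29 code, under the label of bleeding. The ulcer overlap adds false positives only.

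**Working it through.** The plan states no figure to reproduce on this point, so the check compares the two code lists.

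**Inputs.** The Bleeding row of Table 1 and the ulcer disease row of Table 3 (both section 9.3.3), and the planning cohort size in section 9.5.

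**Step 1: expand the ranges and compare.**

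| Category | Table 1, Bleeding | Table 3, Ulcer disease | Sub-code also listed in the Bleeding row |
|---|---|---|---|
| K25 | whole category | whole category | K250 |
| K26 | whole category | whole category | K260 |
| K27 | whole category | whole category | K270 |
| K28 | whole category | whole category | K280 |
| K29 | whole category | not listed | K290 |

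Four of the five whole K categories in the Bleeding row are also ulcer disease in Table 3. K29 is not among them, and the protocol gives it no other label.

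**Step 2: test whether anything narrows the row.** Each of the five sub-codes lies inside a category that is already listed whole. Adding a subset to the set that contains it changes nothing, so the sub-codes have no effect while the range stands. The prescription column adds no condition.

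**Step 3: consequence for a patient.** A K25-K28 code sets ulcer disease to yes through Table 3 and history of bleeding to yes through Table 1. No K25-K28 code can yield ulcer disease without a history of bleeding.

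**Step 4: direction and size.** Let p be the share of the cohort correctly flagged by the row, and q the share flagged only because of a K25-K29 code that does not denote a bleed. Then

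- reported prevalence = p + q
- bias = q, which is zero or positive
- ratio of reported to correct = 1 + q/p

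The documents give neither p nor q, so neither the bias nor the ratio can be computed. For scale only, section 9.5 gives the cohort found in the previous study: "The total of these patients was 62,888". Its components agree: 7,441 + 23,412 + 16,026 + 12,779 + 3,230 = 62,888. Each percentage point of q would be 62,888 × 0.01 = 628.88, or about 629 patients wrongly shown as having bled.

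**Step 5: what remains if the range is removed.** K250, K260, K270, K280, K290, K922, R04, R31, R58, S063, S064, S065 and S066. Whether these include every code for a bleeding ulcer cannot be settled from the documents, which do not say what the individual sub-codes denote.

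**The case against.** The best defence is that little depends on this variable. Section 9.5 says "This study plans no formal hypothesis testing", section 9.7.1 plans no adjusted model, and section 9.3.1 treats all anticoagulants as one exposure group. History of bleeding is not an eligibility criterion in section 9.2. No incidence rate, person-time or confidence interval uses it. All of this stands and limits the point to a descriptive table.

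A second defence is that a broad, sensitive definition may have been intended. That is possible, but the protocol gives no reason for it, and the label in the table would still be wrong for patients with an ulcer and no bleed.

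A third is that section 9.9 concedes that the sensitivity and specificity of the study's definitions are unknown. That statement is general and its examples are outcome codes. It does not cover a conflict between two of the protocol's own tables, which can be corrected before programming.

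A reader might also infer more than the documents support:

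- *That the major-bleeding rates are inflated.* Section 9.3.3 assigns Table 1 to clinical history, and section 9.3.2.1 does not cite it. Table 1 holds the only list labelled bleeding, so reuse is conceivable, but the documents do not say that it will happen.
- *That the redundant sub-codes show that a narrow definition was meant.* Redundant listing is common in this protocol. The Trauma row gives S00-S09 and then S065, S066, S081 and S089, and repeats S480 and S481. Redundancy is therefore no evidence of intent.
- *That prior bleeding becomes largely a copy of ulcer disease, or is overstated by some multiple.* The row also contains K922, R04, R31, R58 and S063 to S066, and no frequencies are given. Any multiple would only return the values assumed for p and q.
- *That the protocol calls all of K25-K29 ulcer disease.* Table 3 stops at K28.

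**Conclusion.** The point holds for the history-of-bleeding covariate. Followed exactly, Table 1 flags every patient with a K25-K28 code as having bled, while Table 3 treats those categories as ulcer disease. The tabulated prevalence of prior bleeding, overall and in each age group, is biased upward by an amount that cannot be computed from the documents.

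This rests on two assumptions: that the tables are programmed as written, and that some patients in the cohort have a K25-K28 code without a bleed and no other code in the row. For K29 the documents show only that the whole category and one of its sub-codes both appear. Whether it adds false positives depends on the code dictionary.

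Any effect on outcomes (2) and (3) is conditional. If the list were reused there, a fracture or trauma admission that also carries a non-bleeding ulcer code could be counted as a major bleed.

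**What to change.** In the Bleeding row of Table 1, replace the range K25-K29 with bleeding-specific sub-codes only. Start from K250, K260, K270, K280 and K290, and add any other haemorrhage-specific sub-codes within K25-K29 that the sponsor confirms against the code dictionary. Do not assume that the five listed codes are complete, since too short a list would replace over-counting with under-counting. Table 3 needs no change.

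State in section 9.3.2.1 which codes define bleeding for outcomes (2) and (3). If the Table 1 list is to serve there, use the corrected list.

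The cost is a dictionary check and a code-list edit before programming. The downside is that bleeds recorded only at three-character level are missed. Tabulating prior bleeding under both the broad and the narrow definition would show how much the choice matters, at the price of one extra row in the baseline table.
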